4.3.3. Vaccine and Exposure to Infections Guidelines

It is recommended that all study participants should be up-to-date with respect to standard of care vaccinations (as defined by their country health ministry) or JIA guidelines.

Vaccination with live components (e.g. live attenuated influenza vaccine, MMR (measles, mumps, and rubella) vaccine, or MMR-V (measles, mumps, rubella and varicella) vaccine) is prohibited within the 6 weeks prior to first dose of study drug. At the discretion of the investigator, subjects may be vaccinated with a live or live-attenuated vaccine at any time during the study only if tofacitinib is discontinued for a minimum of 6 weeks prior to vaccination and a minimum of 6 weeks after vaccination.

Inactivated vaccines, including inactivated influenza vaccine, pneumococcal conjugate vaccine and pneumococcal polysaccharide vaccines, may be administered to study subjects during the conduct of the study.

Administration of non-live COVID-19 vaccines that are fully approved or approved for emergency use is permitted during the study, provided that the vaccination is not part of another clinical study. Examples include, but are not limited to, mRNA vaccines, adenovirus vector vaccines and inactivated COVID-19 vaccine. If a participant receives a non-live COVID-19 vaccine during the study, it should be recorded as a concomitant medication and standard AE collection and reporting processes would be followed.

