5.2.1. Tofacitinib Temporary Withholding

Dosage of tofacitinib may be temporarily discontinued for up to 28 consecutive days, for more severe cytopenias, for infections which do not meet criteria for serious infections (those requiring parenteral antimicrobial therapy or hospitalization), for surgical procedures or other moderately severe AEs. Additionally, tofacitinib must be temporarily discontinued for a minimum of 6 weeks prior to giving live or live-attenuated vaccines. Tofacitinib would then be restarted a minimum of 6 weeks after receiving the vaccine. Withholding of study drug is not necessary when administering non-live vaccines, including inactivated influenza vaccine and non-live COVID-19 vaccines.

Per Amendment 10, for subjects with suspected venous thromboembolism, treatment with tofacitinib should be temporarily withheld while the subject is evaluated. If venous thromboembolism is confirmed, discontinue treatment with tofacitinib and withdraw the subject from the study (see [Section 6.2.6: Subject Withdrawal](#)).

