Tofacitinib: The dose of tofacitinib may be decreased or discontinued for subjects who continue to have inactive disease for at least 24 consecutive weeks after receiving the last dose of MTX/leflunomide. The dose is to be reduced by 5 mg every 12 weeks as long as the subject's disease remains inactive. The evening dose should always be reduced before the morning dose. For example, a subject receiving a total daily dose (TDD) of 10 mg (5 mg BID) prior to tapering will step down to a TDD of 5 mg by taking 5 mg in the morning and 0 mg in the evening. If they continue to have inactive disease for a least 12 consecutive weeks while receiving a TDD of 5 mg, the 5 mg morning dose may also be discontinued.

Subjects will be followed for 6 months (24 weeks) after tofacitinib is discontinued by returning to the site for schedule visits and completing all visit assessments.

If at any time during the tapering process or after discontinuation of tofacitinib, the subject is not able to maintain the inactive disease status (as defined in the protocol [Section 7.1.7](#)), concomitant JIA therapies (eg, oral corticosteroid, methotrexate/leflunomide) and tofacitinib can resume if appropriate according to investigator judgment.

Tofacitinib will restart at 5 mg BID. Concomitant JIA therapies and doses should be adjusted at the discretion of the investigator.

Appendix 5. Estimated Glomerular Filtration Rate (GFR) and Creatinine Clearance (CrCl) Calculations

1. eGFR will be evaluated at screening to determine if a subject is eligible.

The Bedside Schwartz GFR equation²¹ will be used to estimate glomerular filtration rate (eGFR) from serum creatinine (creatinine methods with calibration traceable to IDMS).

$$\text{eGFR (mL/min/1.73 m}^2\text{)} = 0.413 \times (\text{Ht} / \text{Scr})$$

Height (Ht) in cm;

Serum creatinine (Scr) in mg/dL

2. Creatinine clearance (CrCl) will be evaluated at every study visit.

- (i) Participants <12 years of age

The Modified Schwartz equation²⁷ will be used to estimate creatinine clearance in participants < 12 years of age

$$\text{CrCl (mL/min/1.73 m}^2\text{)} = (\text{K} \times \text{Ht}) / \text{Scr}$$

K (proportionality constant):

Female Child < 12 years of age: K = 0.55

Male Child < 12 years of age: K = 0.70

- (ii) Participants ≥ 12 years of age

The Cockcroft-Gault equation²⁷ will be used to estimate the creatinine clearance for participants ≥ 12 years of age.

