- Components: cardiovascular death, non-fatal myocardial infarction, and non-fatal stroke.
- Including SMQs: Hepatic failure, fibrosis, and cirrhosis, and other liver damage-related conditions; and Hepatitis, non-infectious.
- Including Acute renal failure SMQ.
- Adjudicated by an internal review committee.

Incidence Rates (IRs) will be calculated and presented in 100 subject-years and defined as follows:

$$\text{IR} = 100 * \frac{\text{Number of Unique Subjects with Event during the Risk Period (RP)}}{\text{Sum of Event Exposures for all Subjects (Subject-Years of Exposure)}}$$

The numerator of the IR will include subjects counted only once as soon as they experience a first event during their individual risk period (RP) defined below.

The denominator will be the sum of the times to event for those who experience an event during the risk period and the lengths of risk periods for those who do not experience an event. If a subject experiences multiple instances of the same event, the time to first occurrence of the event will be considered.

In general, a subject is considered at risk to experience an AE while on tofacitinib treatment and within 28 days of stopping tofacitinib treatment. Thus, the risk period extends from the subject's first dose of tofacitinib up to the date of last dose of tofacitinib + 28 days.

For the final analysis, the RP is defined as:

$$\text{RP} = \min(\text{last dose date} + 28 \text{ days}, \text{last contact date}) - \text{first dose date} + 1 \text{ day}.$$

The last contact date will be the maximum of (AE start date, AE stop date, last study visit date, withdrawal date). If a subject is dead, the last contact date will be the death date.

For an interim analysis with a data cutoff date, the RP is defined as:

$$\text{RP} = \min(\text{last dose date} + 28 \text{ days}, \text{last contact date}, \text{data cutoff date}) - \text{first dose date} + 1 \text{ day}.$$

95% CI (corresponding to  $\alpha=0.05$ ) for this IR will be calculated based on the assumption that the actual count of cases (i.e., unique subjects with events) arises from an exact Poisson distribution. The approach used in Daly (1992) describing the calculation of exact confidence limits will be used. If  $x$  denotes the actual number of subjects with events, the (1

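### SAP 6.6 counts drug-free time beyond 28 days as exposure in subjects who stop tofacitinib and restart, which biases downward the rates of events that force withdrawal

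*SAP*

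**What the plan says.** SAP 6.6 gives the principle first: "In general, a subject is considered at risk to experience an AE while on tofacitinib treatment and within 28 days of stopping tofacitinib treatment". It then draws the operational rule from it: "Thus, the risk period extends from the subject's first dose of tofacitinib up to the date of last dose of tofacitinib + 28 days". As a formula, the risk period (RP) at the final analysis is min(last dose date + 28 days, last contact date) − first dose date + 1 day. The interim version adds the data cutoff date to the minimum. The denominator, labelled as subject-years of exposure, sums times to first event and "the lengths of risk periods for those who do not experience an event". Nothing is subtracted for interruptions.

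The protocol describes three kinds of stop:

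- Section 5.2.1, for cytopenias, non-serious infections, surgery and other moderately severe adverse events: "Dosage of tofacitinib may be temporarily discontinued for up to 28 consecutive days".
- Sections 4.3.3 and 5.2.1, for live vaccines, which are allowed "only if tofacitinib is discontinued for a minimum of 6 weeks prior to vaccination and a minimum of 6 weeks after vaccination". Section 5.2.1 then provides for restart.
- Appendix 4, for subjects with sustained inactive disease who taper tofacitinib to zero: "Subjects will be followed for 6 months (24 weeks) after tofacitinib is discontinued by returning to the site for schedule visits and completing all visit" […]. Tofacitinib may be resumed if inactive disease is lost.

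**The concern.** The step from the at-risk principle to the formula is valid only if nobody stops for more than 28 days and then restarts. The second and third kinds of stop above do exactly that, and they are written features of the study rather than deviations. For such subjects the denominator includes time that the SAP's own principle places outside risk.

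The formula also makes the status of a drug-free day depend on what happens later. The same days are excluded if the subject never restarts and included if the subject does. Under Protocol 8.5.1, 5.2.1, 6.2.6 and Appendix 8, a serious infection, a confirmed venous thromboembolism or a malignancy (apart from the listed skin and cervical exceptions) ends participation. A subject with such an event late in a gap therefore does not restart, and neither the late gap time nor the event is counted. A subject who passes through the gap without one may restart, and the whole gap is then counted. This is immortal time: for these endpoints the added person-time is event-free by construction. Long-term safety is the primary objective, and these are among its key rates.

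**Working it through.** The documents state no incidence rate, event count or number of interrupted subjects, so there is no plan figure to reproduce. The check applies the SAP formula to the gaps the protocol allows and compares it with an RP that keeps only dosing intervals plus 28 days each. For one gap followed by restart, the excess is max(0, gap − 28 days).

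1. **Excess per gap.**
   - Hold of up to 28 days: 28 − 28 = 0.
   - Live vaccine, at least 6 + 6 = 12 weeks (84 days): 84 − 28 = 56 days, so at least 8 weeks.
   - Taper to zero with restart at the end of the 24-week follow-up (168 days): 168 − 28 = 140 days, so up to about 20 weeks. Earlier restart gives less; restart at week 8 adds 8 − 4 = 4 weeks.

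2. **Dependence on the future.** Take first dose on day 1 and a stop on day 400.
   - Never restarted, followed to day 568: RP = min(428, 568) − 1 + 1 = 428 days. Late drug-free time is excluded, as intended.
   - Restarted on day 568, last dose day 765, last contact day 793: RP = 793 days. Days 429 to 567 (139 days) are now counted.
   - At an interim cutoff on day 500 this second subject has RP = 428 days. Days 429 to 500 are outside the interim RP but inside the final one.

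3. **Single subjects, in weeks, ignoring the one-day term.**
   - 104 on, 24 off, 52 on: SAP 104 + 24 + 52 + 4 = 184; interval-based (104 + 4) + (52 + 4) = 164; ratio 184/164 = 1.12.
   - 52 weeks from first to last dose with a 12-week vaccine stop: SAP 52 + 4 = 56; interval-based 56 − 8 = 48; ratio 56/48 = 1.17.

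4. **Cohort.** Assume 5 to 20% of subjects have one 24-week gap and the mean RP is 156 weeks. The excess share of subject-years is 0.05 × 20/156 = 0.6% to 0.20 × 20/156 = 2.6%.

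5. **Wider assumptions.** Take N = 340 (Protocol 9.1), 5 to 40% of subjects with one gap, and no events in the gap. With last dose at 3 years (RP 1123 days), rates are understated by 0.2 to 2.0% for 84-day gaps and 0.6 to 5.0% for 168-day gaps. With last dose at 1 year (RP 393 days) and 84-day gaps, the range is 0.7 to 5.7%.

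   The 1-year case with a 168-day gap is not a realistic scenario. For a subject on 5 mg BID without corticosteroids or MTX/leflunomide, Appendix 4 implies 24 weeks inactive + 12 weeks at the reduced dose + a 24-week gap = 60 weeks. It would fit only if inactive time in the index study counted, and Appendix 4 says that only in its corticosteroid paragraph.

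6. **Against sampling error.** With 10 events, 3 years and 20% of subjects with a 168-day gap, the SAP denominator is 340 × 1123/365.25 = 1045.4 subject-years. The interval-based one is (340 × 1123 − 68 × 140)/365.25 = 1019.3. With the SAP's exact Poisson limits, the rates per 100 subject-years are 0.96 (0.46 to 1.76) and 0.98 (0.47 to 1.80).

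**The case against.** The strongest case is that this changes no conclusion. The study is descriptive, the cohort shift is small beside the confidence interval in step 6, and the share of subjects with a long gap is not in the documents. Live vaccination is discretionary, the route to zero tofacitinib is slow, and a 24-week gap with restart is near the maximum. All of this stands and limits the weight of the point.

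It can also be said that the SAP hedges its principle as general and that stopping may mean final cessation, which makes a first-to-last-dose period a stated and reproducible choice. That is a fair reading. It does not remove the asymmetry in step 2.

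A further objection is that interval-based time would drop, say, a lymphoma found in week 6 of a vaccine stop from the headline rate. It would, but so does the current formula: malignancy ends participation, the last dose stays before the gap, and week 6 lies beyond last dose + 28 days. For these endpoints the change alters only the denominator.

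Two stronger readings are tempting, and the documents do not support them. A reader might infer that every incidence rate is diluted. Counting stops at the first event, so a subject whose event precedes the gap contributes no gap time. For events that allow restart, gap events can enter the numerator, so the direction depends on an unknown off-drug rate. A reader might also infer that off-drug visits and flares distort the persistence-of-efficacy results. SAP 6.2 does not separate them, but tapering is part of the protocol's strategy and SAP 3.2 and Appendix 1.8 report tapering outcomes as separate endpoints. Clinical remission requires being on medication, though tofacitinib is not named. The by-visit summaries describe the treat-and-taper course, so including those visits is a choice rather than an error.

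**Conclusion.** The point holds for the safety risk period, and only for subjects who stop for more than 28 days and restart. Holds of 28 days or less add nothing. The downward direction for serious infection, venous thromboembolism and malignancy follows from the withdrawal rules, provided they are followed; for other events it cannot be stated. The per-gap excess comes directly from the protocol's own intervals. The cohort figure rests on an assumed gap prevalence and mean follow-up, and would be larger if gaps proved common or follow-up short. The likely effect is a small understatement of some rates, worth correcting because it concerns the primary objective and is cheap to remove.

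**What to change.** In SAP 6.6, define the RP as the union of dosing intervals, each extended by 28 days and truncated at last contact (and at the cutoff date for interim analyses). State that the numerator counts the first event starting inside that time and that time to event counts only those days. List events that start in excluded gap time separately, and keep the continuous RP as a sensitivity analysis. No clinical rule changes.

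The cost is slightly fewer subject-years and some programming. It needs start and stop dates for each dosing period: SAP Appendix 1.8 says taper data are on the CRF, and the team should confirm that vaccine interruptions are dated too. Optionally, flag efficacy visits and flares that fall off tofacitinib. That would be a supportive display, not a correction.

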## 2.2. Study Design

This is a Phase 2/3, long term, open-label, follow-up study. Subjects will have previously participated in qualifying/index study in the tofacitinib JIA program. Those who have already completed such participation and enroll outside the 14-day window following completion of the End of Study (EOS) Visit of the qualifying/index study will participate in a Screening Visit to determine eligibility. A Baseline Visit will then occur within 28 days after the Screening Visit. For subjects who are completing participation in a qualifying study of tofacitinib and enrolling on the same day of the EOS Visit of the qualifying/index study, the EOS Visit of the qualifying/index study can be combined with the Screening and Baseline Visits for this study. The subjects who enroll within the 14-day window following completion of the EOS Visit of the qualifying/index study will participate in a combined Screening and Baseline Visit for this study. After the Baseline Visit, visits will occur at 1 month (1 month=30 days) and 3 months, then every 3 months thereafter as long as the subject remains in the study.

Approximately 340 participants are projected to enroll into this open label extension study after completing a qualifying/index study (i.e., A3921103, A3921104 or A3921165) in the JIA program.

For subjects who entered this study from the A3921103 and A3921104 qualifying/index studies, their participation in this study ends after the first global marketing approval of tofacitinib for the treatment of polyarticular course Juvenile Idiopathic Arthritis (pJIA) in any country.

This study will end once the last subject, and all other subjects, who entered from study A3921165 have completed approximately 1 year in this study, or after the first marketing approval of tofacitinib for the treatment of systemic JIA, whichever comes first.

The total duration of an individual subject's participation may vary depending upon when they entered the trial.

**Applicable to Canadian Investigator Sites Only:** The duration of subject participation will be restricted to 3 years, unless, in the Investigator's opinion, it is in the subject's best interest to continue receiving tofacitinib (to be determined on a case-by-case basis and in consultation with the Sponsor).

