$-\alpha) \times 100\%$  confidence limit,  $x_L$  the lower confidence limit and  $x_U$  the upper confidence limit, then the following formula yields values for  $x_L$  and  $x_U$ ,

When  $x > 0$ ,

$$x_L = 0.5 * \chi^2(\alpha/2; 2x) \text{ and } x_U = 0.5 * \chi^2(1 - \alpha/2; 2x+2),$$

When  $x = 0$ ,

$$x_L = 0 \text{ and } x_U = 0.5 * \chi^2(1 - \alpha/2; 2x+2).$$

In the above notation,  $\chi^2(p; n)$  represents the  $p^{\text{th}}$  quantile of the chi-square distribution with  $n$  degrees of freedom. Once  $x_L$  and  $x_U$  are obtained, they are to be adjusted for the at-risk population per 100 subject-years by multiplying by 100.

In addition, all adjudicated events will be listed.

Additionally, Potential Hy's Law Cases, defined as patients with AST or ALT  $\geq 3$  x the upper limit of normal (ULN) concurrent with a total bilirubin  $\geq 2$  x ULN, will be summarized.

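### SAP 6.6 scales the exact Poisson count limits by 100 but leaves out the subject-years divisor that its own incidence-rate formula uses

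*SAP*

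**What the plan says.** SAP Section 6.6 introduces the rates with "Incidence Rates (IRs) will be calculated and presented in 100 subject-years and defined as follows". The formula is 100 times the number of unique subjects with an event in the risk period, divided by "Sum of Event Exposures for all Subjects (Subject-Years of Exposure". That divisor is specific to each event: "The denominator will be the sum of the times to event for those who experience an event during the risk period", plus the full risk periods of subjects without the event.

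The section then specifies a 95% confidence interval for this rate. It assumes that "the actual count of cases (i.e., unique subjects with events) arises from an exact Poisson distribution" and gives the usual chi-square expressions for the lower limit `x_L` and the upper limit `x_U`, with `x_L` set to 0 when no subject has an event. The only step from these count limits to the rate scale is that "they are to be adjusted for the at-risk population per 100 subject-years by multiplying by 100".

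**The concern.** `x_L` and `x_U` are limits for an expected number of subjects, and neither contains an exposure term. The point estimate divides by subject-years. The stated conversion of the limits does not, so estimate and interval end up on different scales. Multiplying by 100 cannot adjust for the population at risk: the limits come out the same whether 100 or 1700 subject-years were observed.

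The primary objective is long-term safety and no hypothesis is tested. These are the only confidence intervals the SAP specifies for that objective. They apply to every row of the Section 6.6 event list, including deaths, serious infections, malignancy, MACE, VTE and MAS. Several of these may have few or no cases, and with no cases the upper limit is the informative result.

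**Working it through.** The SAP gives no numerical rate, interval or exposure, so there is no printed figure to reproduce. The check is of the rule itself.

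**Inputs**
- α = 0.05, two-sided, and the count-limit formulas: SAP 6.6.
- E, the sum of event exposures in the IR denominator: defined in SAP 6.6, size not given. *Assumption:* 340 to 1700 subject-years. SAP 2.2 says "Approximately 340 participants are projected to enroll into this open label extension study"; 340 × 1 year = 340 and 340 × 5 years = 1700. E = 100 stands for a small subset.

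**Step 1: count limits.** `x_L` = 0.5 × χ²(0.025; 2x) and `x_U` = 0.5 × χ²(0.975; 2x + 2).
- x = 0: 0 and 3.689
- x = 1: 0.0253 and 5.572
- x = 5: 1.6235 and 11.668

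Each non-zero limit leaves 0.025 in its Poisson tail, so the count formulas are correct.

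**Step 2: conversion as written.** 100 × `x_L` and 100 × `x_U`. For x = 5 this is 162.3 to 1166.8 at any exposure. For x = 0 the upper limit is 368.9.

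**Step 3: conversion consistent with the IR formula.** 100 × `x_L` / E and 100 × `x_U` / E. For example, with x = 5 and E = 340: 162.35 / 340 = 0.48 and 1166.8 / 340 = 3.43.

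| x | E (assumed) | IR per 100 SY | Limits with divisor | Limits as written |
|---|---|---|---|---|
| 0 | 340 | 0 | 0 to 1.08 | 0 to 368.9 |
| 0 | 1000 | 0 | 0 to 0.37 | 0 to 368.9 |
| 0 | 1700 | 0 | 0 to 0.22 | 0 to 368.9 |
| 5 | 100 | 5.00 | 1.62 to 11.67 | 162.3 to 1166.8 |
| 5 | 340 | 1.47 | 0.48 to 3.43 | 162.3 to 1166.8 |
| 5 | 1000 | 0.50 | 0.16 to 1.17 | 162.3 to 1166.8 |
| 5 | 1700 | 0.29 | 0.10 to 0.69 | 162.3 to 1166.8 |

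**Step 4: size of the discrepancy.** For a non-zero limit, (100 × `x_L`) / (100 × `x_L` / E) = E, and likewise for `x_U`. At x = 0 the lower limit is 0 under either rule.

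**Step 5: does the interval as written contain its own IR?** The IR falls below the lower limit when 100x / E < 100 × `x_L`, that is, when E > x / `x_L`. For x = 1 the threshold is 1 / 0.0253, about 39.5 subject-years. For x = 5 it is 5 / 1.6235, about 3.1. At x = 0 the IR is 0 and lies inside the interval.

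**The case against.** The best defence is that the intent is clear. The interval is described as belonging to the IR, the conversion sentence speaks of the at-risk population and of 100 subject-years, and the IR formula with its divisor stands in the same section. Read together, these can coherently mean only 100 × `x_L` / E and 100 × `x_U` / E. A literal implementation would also usually expose itself: at E = 340 it would print an IR of 1.47 beside limits of 162 to 1167. In addition, SAP 5.1 gives the study no hypotheses or decision rules, and much of the safety reporting in SAP 6.1 does not use this sentence.

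This lowers the practical risk, but it does not make the written operation correct. Section 2 of the SAP presents the document as the detailed methodology, and its explicit conversion step should not have to be overridden by inference. Visible failure is not guaranteed either, because with no events the interval 0 to 368.9 does contain its estimate. Nor does the sentence say which exposure to divide by. A programmer who repairs it unaided might use total exposure instead of the event-specific sum. For frequent events such as TEAEs, where many subjects stop contributing time early, that would give limits that look plausible and are wrong.

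A reader might infer that every safety interval in this study is, or will be, wrong. The documents do not support that: they show an incorrect instruction and no computed interval.

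**Conclusion.** The conversion rule is wrong as written. If it is programmed literally, each non-zero limit is too large by a factor E. For most non-zero counts at realistic exposure, the interval then excludes its own IR. The algebra needs no assumption about exposure. The illustrated rates and limits rest on the assumed range for E.

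Three stronger statements do not hold:
- The factor is not one common total exposure. Time is cut at the first event, so E differs by event.
- The interval does not always miss its estimate. It contains it at x = 0, and at x = 1 when E is below about 39.5 subject-years.
- The error does not reach the point-estimate IRs or the chi-square count limits, which are correctly specified. The lower limit at x = 0 is also unaffected.

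**What to change.** Replace the conversion sentence in SAP 6.6 with:

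> The confidence limits for the IR are 100 × x_L / E and 100 × x_U / E, where E is the event-specific sum of event exposures in subject-years used in the IR denominator for that event.

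Then confirm that the programs for the incidence-rate tables use this same E for estimate and limits. A useful test is one event with a non-zero count and one with none. The cost is one sentence and a short program check. Design, data collection and the chi-square formulas stay as they are.
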